8.1 Adverse Event (AE) Reporting Requirements for this study

- All adverse events that meet the definition of serious (not to include elective surgeries)
- All AE's related to operative site, regardless of seriousness

See Adverse Event Decision Tree - Figure 1

Adverse Event Reporting Period

The study period during which adverse events must be reported is normally defined as the period from the initiation of any study procedures to the end of the study treatment follow-up. In other words, the start of study procedures is considered to be the point of consent. Therefore, any adverse events which fit the protocol defined reportable events must be reported from the time of obtaining consent throughout the study duration.

At each contact with the subject, the investigator must seek information on adverse events by specific questioning and, as appropriate, by examination. Information on protocol defined adverse events should be recorded immediately in the source document, and also in the appropriate adverse event module of the case report form (CRF). All clearly related signs, symptoms, and abnormal diagnostic procedure results should be recorded in the source document, though they should be grouped under one diagnosis. The clinical course of each event should be followed until resolution or until it is determined at the end of the study that the adverse event will not resolve.

During the medical record review of the retrospectively enrolled cases, any operative site adverse events will be documented as per the usual procedure. For prospective follow-up, these cases will adhere to the adverse event reporting described above.

General Physical Examination Findings

At screening for inclusion into the study, any clinically significant abnormality should be recorded as a preexisting condition. During the study, any new clinically significant findings/abnormalities that meet the definition of a protocol defined adverse event must also be recorded and documented as an adverse event.

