9.4.5 Censored Cases

Data for patients where a protocol deviation occurred which could affect patient outcome will be censored from the Efficacy and Safety Patient Populations. They will be reported on separately.

If a case receives a unicompartmental knee arthroplasty in the contralateral compartment of the study knee, this case will be considered a deviation and censored from analysis for all areas except survivorship. This case will be included in the survivorship analysis only.

10 Study Procedures

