10.3 Early Withdrawal of Subjects

When and How to Withdraw Subjects

Termination Reason

In the event that the subject is discontinued by the investigative site after discussion with the sponsor prior to the final study evaluation, the subject is notified that they are no longer in the study and a Study Termination CRF will be completed. The following is a list of reasons for which subjects may be terminated, and the date of termination that should be used on the Study Termination CRF in each situation. This list is not all inclusive:

Date of Termination

Tommation Roadon	Date of Fornination
Death	Date of death
Investigative site termination	Date of study close-out visit
Lost to follow-up	Date Stryker termination approval given
Voluntary withdrawal	Date subject notified site of withdrawal

Termination Reason

Revision/removal of study device
Study device not implanted
Surgery not performed

Date of Termination

Date of revision/removal procedure

Date of surgery

Date Stryker termination approval given

If the subject fails to return for their follow-up appointments, every effort should be made to contact the subject to assess his/her health status. If after attempting to contact the subject through three documented phone calls and a certified letter, the subject still does not respond, he/she will be considered lost to follow-up. A Study Termination CRF will be completed only after notifying Stryker of the subject's status and being given approval to terminate.

Study Completion

When a subject completes the study according to protocol, including the final study evaluation, a Study Termination CRF will be completed and the termination date will be the date of the subject's last evaluation.

11 Data Management

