- Patients with major deformity affecting the mechanical axis of the knee or neuromuscular disorders compromising motor control and/or stability.
- Any mental or neuromuscular disorder, which would create an unacceptable risk of prosthesis instability, prosthesis fixation failure or complications in post-operative care.
- Skeletal immaturity.
- Ligamentous instability such that the postoperative stability afforded by the unicompartmental knee prosthesis would be compromised such as multidirectional/ACL instability.
- Untreated damage to the contralateral compartment or the ipsilateral knee not being replaced by a prosthesis.
- 10. Untreated deterioration or destruction of the patello-femoral joint.
- 11. Severe deformity and/or recurrent subluxation of the knee joint.
- Obesity. An overweight or obese patient can produce loads on the prosthesis which can lead to failure of fixation of the device or failure of the device itself.
- 13. Severe tibial bone loss/deformity (over 15 degrees varus).

.

QIN 4388, Ver. AB EEN Release Date: Apr 27, 2 101N4388 FP MAIN Date: Aug 03, 2018 15:41:17 GM/T9/2018 2:23:48 PM

Procautions

Before clinical use, the surgeon should thoroughly understand all aspects of the surgical procedure
and limitations of the device. The surgeon should instruct the patient in the limitations of the prosthesis,
including, but not limited to, the impact of excessive loading through patient weight or activity, and be
taught to govern their activities accordingly. If the patient is involved in an occupation or activity that
includes substantial walking, running, lifting, or muscle strain, the resultant forces can cause failure of
the fixation, the device, or both. The prosthesis will not restore function to the level expected in normal
healthy bone, and the surgeon must instruct the patient not have unrealistic functional expectations.

- Appropriate selection, placement and fixation of the knee components are critical factors that affect
 implant service life. As in the case of all prosthetic implants, the durability of these components is
 affected by numerous biological, biomechanical and other extrinsic factors, which limit their service life.
 Accordingly, strict adherence to the indications, contraindications, precautions and warnings for this
 product is essential to potentially maximize service. The surgeon should warn the patient about these
 limitations.

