Reference # Lot Code # Femoral Component: Tibial Component / Metal Tray: Tibial Insert: K. SOFT TISSUE RELEASED: (Check All That Apply) None	N. COMPARTMENT REPLACED: (Check One) Medial Lateral O. ACL INTACT? (Check one) Yes No* *If No, complete Protocol Deviation and Study Termination forms. P. INTRAOPERATIVE COMPLICATION?: (Check one) Yes* No *If Yes, Complete an Adverse Event Form for Each Complication Q. AMBULATORY STATUS AT DISCHARGE: (Check One) Crutches Wheelchair Walker Other: (specify) R. DISCHARGED TO: (Check One) Skilled Nursing Facility Chronic Care Center Rehabilitation Unit Home Other: (specify)
Component minutes Placement:	Discharge Date: D D M M M Y Y Y Y
INVESTIGATOR NAME (PRINT): INVESTIGATOR SIGNATURE: DATE: // // // // // // // // // // // // //	For Stryker Use Only Stamp Date Received: Entry Verification Monitored

	R Outcomes Study Page 1 of 2 CAL DETAILS
[name]	PATIENT ID: 6 6 Study # Site # Subject #
GENERAL INFORMATION PATIENT INITIALS: (If there is no middle initial please use "-")	Study # Site # Subject # SURGERY DATE: D D M M M M Y Y Y Y Y
OPERATIVE SIDE: Right Left (Check One)	
I. SURGICAL DETAILS	
A. TYPE OF ANESTHESIA: (Check all that apply) General	E. NAVIGATION USED? Yes* No
☐ Spinal	*If Yes, complete the following: System Used/Manufacturer
☐ Epidural	Software Version
☐ Femoral Block	Intra-op PRE-Implant
☐ Sciatic Nerve Block	Long Limb (Mechanical) Alignment:
G Golding Monte 2.000	O Valgus O Varus
B. LENGTH OF SKIN INCISION:	Tibial Cut Depth: mm
2 INCIDION (Observers) O MIC O Standard	Distal Femur Cut Depth: mm
C. INCISION (Check one) MIS Standard	Tibial Varus/Valgus Angle:
D. SURGICAL APPROACH: (Check one)	
Medial Parapatellar Lateral Parapatellar	Tibial Slope:
Mediai Farapatellai 🔾 Laterai Farapatellai	Long Limb (Mechanical) Alignment:
How far did the quadricep incision go past the	O Valgus O Varus
superior pole of the patella? (Check one)	F. SURGICAL RANGE OF MOTION: Pre-op Extension: Pre-op Flexion:
at level of superior pole	FIG-Up Extension.
above the superior pole up to 1 cm	Post-op Extension: Post-op Flexion:
above the superior pole up to 2 cm	G. BRAND OF CEMENT USED : (Check one)
above the superior pole up to 3 cm	O Simplex P O Palacos O Cobalt
> 3 cm above the superior pole	Other: (Specify)
	H. BONE REMOVED: (Complete for each)
Mid Vastus	Distal Femur: mm Proximal Tibia: mm
Length of VMO Snip: (Check one)	Patella Facectomy Done? O Yes O No
0 0	

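### Item O of the Surgical Details form calls for study termination whenever the ACL is not intact, without limiting this to knees in which the device was not implanted

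*Combined protocol and SAP*

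**What the plan says.** Appendix E, Surgical Details form, item O asks whether the ACL is intact, with the instruction: "If No, complete Protocol Deviation and Study Termination forms". The same form has fields for the components used ("Reference # Lot Code # Femoral Component: Tibial Component / Metal Tray: Tibial Insert") and for the compartment replaced. The next item keeps intraoperative events: "P. INTRAOPERATIVE COMPLICATION?: (Check one) Yes* No *If Yes, Complete an Adverse Event Form for Each Complication".

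Other sections that bear on it:

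- **4.1, criterion 4** requires the ligaments to be clinically intact at entry. Item O records what is found at surgery.
- **8.1**: reportable adverse events "must be reported from the time of obtaining consent throughout the study duration".
- **9.4.3** bases the primary and secondary efficacy analyses on the per-protocol population, which leaves out deviations that could affect outcome. Revision or removal is the secondary parameter (9.1.2).
- **9.4.5** takes such deviations out of the efficacy and safety populations and says: "They will be reported on separately". It keeps one kind of deviation, a later contralateral-compartment UKA, in the survivorship analysis.
- **10.3** lists "Study device not implanted" as its own termination reason. ACL status is not listed, but the list is stated to be open.
- **11.5** treats an eligibility failure as a major deviation to be recorded and reported to the IRB, and does not mention termination.
- **Appendix C** lists among the contraindications: "Ligamentous instability such that the postoperative stability afforded by the unicompartmental knee prosthesis would be compromised such as multidirectional/ACL instability".

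**The concern.** Most deviation rules in this plan act at the analysis stage. An exclusion made there can be undone in a sensitivity analysis or covered in a separate listing. Item O acts on data collection: once a knee is terminated at surgery, later adverse events and revisions are not recorded, and no choice of population brings them back.

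If the device is in place, the knee is still at risk of revision. Section 2.1.2 restricts the main 10-year Kaplan-Meier analysis to prospective cases in order to avoid bias. A rule that removes knees from that cohort on a surgical finding works against that aim, particularly when the finding is related to a labelled contraindication. If such knees fail more often, their absence favours the device.

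**Working it through.** The plan gives no figure on this point, so the main check is to set the passages side by side. The arithmetic afterwards only shows scale.

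**1. Does item O apply to implanted knees?** The line has no implant condition. Non-implantation already has its own termination reason in 10.3 and on the Study Termination form, so an item O limited to those knees would be largely redundant. The component fields do not settle it: for a device that was not implanted, the Study Termination form also asks for the Surgical Details and Protocol Deviation forms, so a completed Surgical Details form does not prove implantation. The wording covers implanted knees; the documents do not say that there were any.

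**2. What is lost if it does?** Events after termination. Item P still yields an adverse event form for intraoperative complications. The Study Termination form asks once whether the device was in place at last contact, which here would be about the time of surgery.

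**3. Which sections does this disturb?**
- 9.4.5: a separate report on these knees would hold nothing beyond the operation.
- 8.1: reporting is to run through the study duration, and item O cuts it short.
- 11.5: an eligibility failure is recorded and reported, with no exit stated.
- 10.3: no strict contradiction, because its list is open. However, it describes discontinuation after discussion with the sponsor, whereas item O is automatic.

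**4. What would the analysis do with full follow-up?** If the finding is treated as a deviation that could affect outcome, 9.4.3 and 9.4.5 drop the knee from the Kaplan-Meier and safety populations anyway. The only survivorship exception is contralateral-compartment UKA. Correcting item O alone would therefore restore the separate report but not the curve; both rules have to change.

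**5. Who is exposed?** Mainly the 80 prospective knees, the last enrolled on 29 January 2018 (3.3). Retrospective candidates are screened against all criteria, and revised knees are excluded, before consent (10.1). Their operative details, including ACL status, are abstracted after consent (7.1, 7.2), so item O could still be triggered there.

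**6. Illustrative size.** From the documents: 80 prospective knees. Assumed: k terminated implanted knees, 10-year revision risk r in those knees and b in the rest.

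Overstatement of 10-year survival = (k/80) × (r − b)

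| k | r | b | Shift (points) | Unseen revisions, k × r | All expected revisions, (80 − k) × b + k × r |
|---|---|---|---|---|---|
| 2 | 30% | 12% | 0.45 | 0.6 | 9.36 + 0.6 = 9.96 |
| 4 | 30% | 12% | 0.90 | 1.2 | 9.12 + 1.2 = 10.32 |

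With b = 10%, the range runs from (1/80) × (20% − 10%) = 0.125 points to (4/80) × (50% − 10%) = 2.0 points. With k = 0 the shift is zero.

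For comparison, the binomial standard error at 12% failure in 80 knees is √(0.12 × 0.88 / 80) = 0.036, or about 3.6 points.

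The primary KSS analysis is little affected, since these knees would be outside the per-protocol population in any case.

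**The case against.** The strongest reply is that item O was meant for knees in which the surgeon found the ACL deficient and did not use the device. Intact cruciates are an inclusion criterion, ACL instability is contraindicated, 12.2 says the device is used according to its labelling, and the forms item O triggers match those required when the device is not implanted. This is plausible, and it means implantation cannot be stated as fact. But the form does not say it, and a site following the form has no instruction to keep an implanted knee.

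Four further points stand:

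- A reader might infer that item O by itself biases the survival curve and the adverse event rates. Sections 9.4.3 and 9.4.5 would exclude these knees even with complete follow-up; item O's own effect is that the data are never collected.
- A reader might infer that no adverse events at all are captured. Item P captures intraoperative ones.
- A reader might infer that the documents predict more failures in these knees. The label contraindicates instability that compromises stability; it gives no failure rate, and a ticked box for a non-intact ACL is not the same as instability.
- Prospective enrollment is closed, so a form change affects few knees, perhaps none. Following knees already terminated would need recontact and possibly renewed consent.

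Appendix E holds sample forms, and 11.4 refers to a completion guide that is not among the documents and may qualify item O. That would be a good answer if the guide does so.

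**Conclusion.** Item O is wrong as written, with small and unknown reach. It orders termination without an implant condition and, read literally, stops collection of later adverse events and revisions in an implanted knee. That cannot be squared with the separate report promised in 9.4.5 and fits poorly with 8.1 and 11.5.

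The documents do not support saying that implanted knees with a deficient ACL have in fact been lost; the count is not given and may be zero. The 0.45 to 0.9 point shift rests wholly on assumed counts and risks, is well below the sampling error of the survival estimate, and arises from item O together with 9.4.3 and 9.4.5. The case for changing it is that uncollected events cannot be recovered later and the correction is cheap.

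**What to change.** 1. Reword item O: *If No, complete the Protocol Deviation form; complete the Study Termination form only if the study device was not implanted.* Reconcile 8.1, 9.4.5, 10.3 and 11.5 with this.
2. Keep implanted knees with a non-intact ACL in adverse event reporting and revision follow-up to 10 years, so that the separate report has content.
3. Extend the survivorship exception in 9.4.5 to these knees, counted from surgery in the prospective cohort, and leave them out of the per-protocol KSS analysis as now.
4. Report how many implanted knees have already been terminated under item O, with last known implant status and its date. Enter the prospective ones in the Kaplan-Meier analysis up to that date. If that is the day of surgery they add almost nothing to the estimate, but the reader can see the number.

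The cost is one line on the form, one sentence in 9.4.5 and visits for at most a few knees. Recontact of knees already terminated takes more effort and may yield only last known status. Reported survivorship may become slightly less favourable.

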Appendix F

Patient Retention Program

- Retention Program Details
- Comprehensive Booklet of all levels
- A sample patient booklet cover page for an individual level

Triathlon® PKR Outcomes Study Patient Retention Program DETAILS

The intent of the program is to provide a subject with a gift equivalent to the level in which they have completed if they decide to withdraw from the study – all points collected at that time point will be redeemed for one gift. A patient can collect up to the maximum of 200 points at the 10-year visit if all visits previously were completed.

The following grid is to assist the sites in understanding the breakdown of the patient retention program:

LEVEL	\$	POINTS	Visit	Visit Windows	Missed Visit Deduction
Α	20	20	2 WEEK VISIT	±1 week	N/a
С	30	30	6 WEEK VISIT	±1 week	10
D	40	40	3 MONTH VISIT	±2 weeks	10
E	50	50	1 YEAR VISIT	±2 months	10
F	75	75	2 YEAR VISIT	±2 months	25
G	100	100	5 YEAR VISIT	±3 months	25
Н	150	150	7 YEAR VISIT	±3 months	50
I	200	200	10 YEAR VISIT	±3 months	50

Please note that Level B was not included since this was only equivalent to \$25 dollars. The interval points increase as the visit intervals occur further out from the date of surgery.

Missed Visits: If a patient has missed one or more visits, then the point value that equates to that patient's last completed visit is used as the base value. The visits that were missed are then deducted from that value using the "Missed Visit Deduction" column. See Scenario #5 for an example.

For example:

Scenario 1: A subject decides to withdraw after he/she has completed their 1-year visit and has stated he/she wants to use all of his/her "accrued" points for one gift.

• The patent would be provided with the Level E Book

Scenario 2: A subject decides to withdraw after he/she has completed their 1-year visit and has expressed that he/she would like to split his/her points into smaller gifts.

• The patient would be provided with a Level A (20) and Level C (30) book.

Scenario 3: A subject decides to withdraw after he/she has completed their 2-year visit and has expressed he/she would like to split his/her points into smaller gifts.

The patient could be provided with the following:

 The Level A (20) and the Level E (50) → the 5 remaining points would be forfeited

> The Level C (30) and the Level D (40) → the 5 remaining points would be forfeited

It is important to note to the subject of their forfeit of these points if he/she chooses this redemption method. Please remind the subject that he/she can submit for a \$75 gift to use all points.

Scenario 4: A subject decides to redeem his/her points at the 1-year visit and would still like to continue in the study.

• The subject would receive the Level E book for completing the 1-year visit. Once he/she reaches the 10-year visit, his/her points from the already redeemed 1-year visit would be deducted and the remainder available for prize redemption.

10-year points 200 – 1-year points 50 = 150 points remain to redeem for gift

Scenario 5: A subject completes his/her 10-year visit but missed the following previous visits: 3 month and 5 year.

- The subject would receive the Level H book, which is worth 150 points. The patient would forfeit 15 points.
- The subject could receive any combination of booklets that did not exceed 165 points.

200 points (completing 10-year visit) – 35 points (see "missed visit column" in table above) = 165 points.

It is important to note to the subject that they may forfeit points depending upon which intervals they miss.
